7.1.3 Pharmacogenetics analysis plan

This analysis will be performed at the end of the trial by Gateway Biotechnology. To identify genetic variants associated with ZNS protection against hearing loss, we will utilize genetic and metabolic data collected from patients in a genetic association study. Variables including sex, age, normalized values (Z-scores) of drug plasma concentration, Z-scores of noise intensity and duration, and Z-scores of hearing functions measured immediately following surgery will be included in the analysis of variance. Single-marker allelic association analyses will be conducted on the two imputed data sets using PLINK v1.07. The data will be analyzed with a logistic regression model on the additive continuous dosage of minor alleles from 0 to 2 to account for uncertainty of imputation. We will combine association results in the two cohorts by performing

a genome-wide inverse-variance weighting meta-analysis using PLINK v1.07, and assuming a fixed-effect model. Functional annotation of top-associated markers will be performed with R package NCBI2R 1.4.6 (http://CRAN.Rproject. org/package=NCBI2R), and key regional association plots of meta-analyzed results will be generated. To confirm whether these variants are specific to ZNS response, we will apply CEP SKAT to analyze genetic associations based on Z-scores of audiogram average threshold shifts and DPOAE amplitudes. All genetic variants, including both common and rare variants, will be included in this association study. Age, gender, drug concentration, and noise duration and intensity will be adjusted for the analysis. The analysis will also be performed using hearing data collected two weeks following surgery. The only differences will be a) using the Z scores of ECochG AP amplitude, latency, and width as well as WIN score, and b) using average audiogram threshold shifts and DPOAE amplitudes at 30 days (+/- 3 days) post-treatment. We will also include metabolite profiling data to support potential genotypic responses to drug treatments. To control for confounding effects, these models will be adjusted for age, gender, and noise duration and intensity. Finally, the control and ZNS-treated comparisons will be performed using post-hoc comparisons with a Bonferroni adjustment for multiple comparison testing. Statistical analyses will be performed using the CEP-SKAT method in R language, and the statistical software SAS version 9.4 for Windows will be used for additional analysis.

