#### 12.5 Pharmacogenetics analysis plan

This analysis will be performed at the end of the trial by Gateway Biotechnology. To identify genetic variants with ZNS protection against hearing loss, we will first use univariate logistic regression analyses to identify potential confounding variables: sex, age, Z-scores of drug concentration, Z-scores of noise intensity and duration, and Z-scores of hearing functions measure immediately following surgery. Single-marker allelic association analyses will be conducted on the two imputed data sets in PLINK v1.07. The data will be analyzed with a logistic regression model on the additive continuous dosage of minor alleles from 0 to 2 to account for uncertainty of imputation. We will combine association results in the two cohorts by performing a genome-wide inverse-variance weighting metaanalysis using PLINK v1.07, and assuming a fixed-effect model. Functional annotation of top-associated markers will be performed with R package NCBI2R 1.4.6 (http://CRAN.Rproject. org/package=NCBI2R), and key regional association plots of meta-analyzed results will be generated. To confirm whether these variants are specific to ZNS response, we will apply CEP SKAT to analyze genetic associations based on Z-scores of audiogram average threshold shifts and DPOAE amplitudes. All genetic variants, including both common and rare variants, will be included in this association study. Age, gender, and noise duration and intensity will be adjusted for the analysis. The analysis will also be performed using hearing data collected two weeks following surgery. The only differences will be a) using the Z scores of ECochG AP amplitude, latency, and width as well as WIN score, and b) using average audiogram threshold shifts and DPOAE amplitudes at 30 days post-treatment. We will also include metabolite profiling data to support potential genotypic responses to drug treatments. To control for confounding effects, these models will be adjusted for age, gender, and noise duration and intensity. Finally, the control and ZNS-treated comparisons will be performed using post-hoc comparisons with a Bonferroni adjustment for multiple comparisons of any ZNS versus none. Statistical analyses will be performed using the CEP-SKAT method in R language, and the statistical software SAS version 9.4 for Windows will be used for additional analysis.

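### The step meant to confirm that variants are specific to zonisamide (ZNS) response names no variant-by-arm test, so a noise-susceptibility variant could be labelled a drug-response variant

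*SAP*

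**What the plan says.** The genetic analysis is in SAP 7.1.3, with a near-identical text in Protocol 12.5.

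- **Aim.** "To identify genetic variants associated with ZNS protection against hearing loss, we will utilize genetic and metabolic data". SAP 2.2.3 and Protocol 2.2 also give a second aim, a genetic risk profile for drilling-induced hearing loss.
- **First stage.** A "logistic regression model on the additive continuous dosage of minor alleles from 0 to 2", one marker at a time. Then: "We will combine association results in the two cohorts by performing" a fixed-effect meta-analysis. The cohorts are not defined.
- **Confirmation.** "To confirm whether these variants are specific to ZNS response, we will apply CEP SKAT to analyze genetic associations", and these associations are "based on Z-scores of audiogram average threshold shifts and DPOAE amplitudes".
- **Covariates for that step.** The SAP says: "Age, gender, drug concentration, and noise duration and intensity will be adjusted for the analysis". The protocol says: "Age, gender, and noise duration and intensity will be adjusted for the analysis". Protocol 12.5 does list drug concentration among the possible confounders to be screened first, but not in this sentence. The SAP's own later adjustment sentence also omits it.
- **Treatment comparison.** The SAP ends: "the control and ZNS-treated comparisons will be performed using post-hoc comparisons with a Bonferroni adjustment for multiple comparison testing". The protocol describes the same step as any ZNS against none. Neither gives its outcome, its model or the role of genotype.

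The markers named in SAP 2.2.3 and Protocol 2.2 are six noise-induced hearing loss genes and two ZNS-metabolism genes.

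**The concern.** A variant is specific to ZNS response if its effect on hearing differs between ZNS and placebo. The confirmatory step, as described, asks only whether the variant is associated with hearing outcome. A variant that makes every cochlea more vulnerable to noise would satisfy it, and the candidate list deliberately includes genes chosen for noise susceptibility.

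The label matters because the documents intend to use it. Associations that are later validated are to guide dose, and Protocol 1.4 foresees using the data in dialogue with the regulator. A susceptibility marker carried forward as a response marker would point the validation study at the wrong question.

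**Working it through.** **1. The plan's own figure.** The genetic plan states no power or error rate. The inputs borrowed here come from the primary sample size (SAP 2.7): 78 per arm, PTS 50% on placebo and 25% on ZNS, one-sided alpha 0.0125, power 80.4%. With the arcsine approximation to Fisher's exact test:

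h = 2 × [asin√((39 − 0.5)/78) − asin√((19.5 + 0.5)/78)] = 0.496

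power = Φ(0.496 × √(78/2) − 2.241) = Φ(0.856) = 80.4%

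Full enumeration of Fisher's test gives 80.7%. The stated figure reproduces.

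**2. What each described analysis estimates.** Let g be allele dosage, T = 1 for any ZNS and 0 for placebo, and let the outcome depend on

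α + βg + γT + δgT

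β is noise susceptibility and δ is ZNS response.

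| Analysis | Quantity tested |
|---|---|
| Variant on outcome, all arms | roughly β + wδ, with w about 156/234 = 2/3 |
| Same, plus arm or drug level as a main effect | still roughly β + wδ |
| ZNS-treated participants only | β + δ |
| Fixed-effect pooling, if the two cohorts were ZNS and placebo | a weighted average, β + wδ |
| Variant-by-arm term | δ |

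Only the last row isolates δ. In every other row, δ = 0 with β ≠ 0 is a true association that the test is built to find.

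**3. Size, binary outcome.** Simulated trials (2,000 to 3,000 per setting) with 78 placebo and 156 ZNS participants, PTS 50% and 25%, and the same variant effect in every arm (δ = 0). Assumed, not in the documents: minor allele frequency 0.3, allelic odds ratio 1.5 or 2.0, two-sided p<0.05, and a single-variant logistic Wald test standing in for CEP-SKAT.

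| Test | OR 1.5 | OR 2.0 |
|---|---|---|
| Variant, all arms | 43% | 86% |
| Variant plus arm main effect | 46% | 88% |
| Variant, ZNS arms only | about 30% | about 70% |
| Variant-by-arm | about 5% | about 5% |

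At odds ratio 1.0 every test rejects in about 5%.

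**4. Dependence on the assumptions** (all arms, variant only):

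| Setting | OR 1.5 | OR 2.0 |
|---|---|---|
| Allele frequency 0.1, p<0.05 | 22% | 54% |
| Frequency 0.3, p<0.00625 (0.05/8 named genes) | 18% | 62% |
| Frequency 0.3, p<0.0001 | 2% | 16% |
| Frequency 0.3, p<5e-8 | at most 0.4% | at most 0.4% |

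**5. Continuous outcome, with the drug-concentration covariate.** 2,000 trials, residual SD 1, allele frequency 0.3, p<0.05, δ = 0. At 0.2, 0.3, 0.4 and 0.5 SD per allele, the test adjusted for age, noise and drug concentration flags the variant in 47%, 84%, 97% and 100% of trials. Using only the outer thirds of the outcome gives 43%, 80%, 96% and 100%. The variant-by-arm test gives 5% to 6%. At 0.4 SD the rate is 97% with or without drug concentration, and 97% when both ZNS arms have measurable levels. Drug level is also a weak stand-in for arm. The calendar footnotes time the sample from the first dose, which is placebo in the post-op arm, so the level there may be near zero if drawn before the second dose.

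**The case against.** The best defence is that the text is undefined rather than wrong. It does not say which arms enter CEP-SKAT, what the two cohorts are, or what the closing comparison tests. That comparison follows the sentences on genotypic response and model adjustment, so it might be meant as a between-arm contrast of genetic results. This stands in part. A reader might infer that treatment is absent from the genetic plan, or that the closing step is shown not to be an interaction test. The documents support neither. The SAP adjusts for drug concentration, and the closing step is unspecified. What they do support is that no variant-by-arm test is named anywhere, and that the step credited with showing specificity cannot show it whichever arms enter.

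Three further points are fair:

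- The risk-profile aim is properly served by a main-effect test, so the defect is confined to the ZNS-protection aim and the specificity sentence.
- The simulation compares power for a real main effect with the error rate for an absent interaction. It illustrates the logic and does not forecast a false-labelling rate. No significance threshold is stated, and a genome-wide one would flag almost nothing.
- The SAP calls the work exploratory, and dosing use waits on validation. No primary efficacy conclusion is touched.

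**Conclusion.** The point holds in a limited form. The specificity claim does not follow from the analysis described, and a noise-susceptibility variant could be labelled a ZNS-response variant. It is tempting to say that such variants would be so labelled. The documents do not support that, because it depends on the variant's effect, the unstated threshold and the undefined closing step.

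The range in step 3 is the upper part of a span that runs down to nearly zero. It rests on the assumed allele frequency, odds ratios and p-value cut-off, and on a single-variant substitute for a set-based test. The argument in step 2 needs none of these. The plan should be changed, but the harm is bounded: the analysis is exploratory in the SAP (the protocol lists it under secondary objectives), and a later study stands between any finding and its use.

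**What to change.** In SAP 7.1.3 and Protocol 12.5:

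1. In all randomised participants, fit outcome on variant + arm (any ZNS against placebo) + variant-by-arm, adjusted for age, sex and noise duration and intensity. For the SKAT analysis, specify the matching set-by-arm interaction test.
2. Call a variant ZNS-response only on the interaction result. Report main effects as noise susceptibility under the existing risk-profile objective.
3. State which arms enter each analysis, define the two cohorts, and give the significance threshold.
4. Either define the closing control-versus-ZNS comparison as this interaction test or say what else it is.
5. Reconcile the covariate lists on drug concentration, between the documents and within the SAP.

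No new data are needed. The single-variant change is two model terms; the set-based version takes more specification and programming. The real cost is power. In the continuous simulation, with a true variant-by-treatment effect of 0.4 SD per allele, no effect on placebo and allele frequency 0.3, the interaction test at p<0.05 succeeds in 44% of trials of 234 subjects, and a stricter threshold would lower that. Few or no variants may be named, and the plan should say so in advance.

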## 2.2 Secondary Objectives

To determine if preoperative ZNS is more effective than placebo at preventing temporary changes in cochlear health, synaptopathy, and degraded speech perception in the contralateral ear of patients undergoing drilling during skull base surgery.

To identify a genetic risk profile associated with drilling-induced hearing loss we will survey known genetic markers associated with NIHL including markers in CDH23, PCDH15, EYA4, MYO1A, KCNMA1 and OTOG (Zhang et al., (2019) and zonisamide (ZNS) metabolism, CYP2C9 and CYP2C19 (Saruwatari et al., 2010). If significant associations are observed and validated in a subsequent clinical study, we will optimize drug dosages based on a subject's genetic profile.

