2.2.3 Exploratory Analysis

To identify a genetic risk profile associated with drilling-induced hearing loss we will survey known genetic markers associated with NIHL including markers in CDH23, PCDH15, EYA4, MYO1A, KCNMA1 and OTOG1 and zonisamide (ZNS) metabolism, CYP2C9 and CYP2C192. If significant associations are observed and validated in a subsequent clinical study, we will optimize drug dosages based on a subject's genetic profile.

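### SAP 7.1.3 adjusts some genetic analyses for plasma zonisamide level and early post-surgery hearing, which may lie on the pathway from genotype to outcome, and its covariate list conflicts with Protocol 12.5

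*SAP*

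**What the plan says.** The genetic targets include noise-susceptibility genes "and zonisamide (ZNS) metabolism, CYP2C9 and CYP2C19" (Protocol 2.2). SAP 2.2.3 gives the intended use: "If significant associations are observed and validated in a subsequent clinical study, we will optimize drug dosages based on a subject's genetic profile". The Protocol lists this aim under secondary objectives; the SAP calls it exploratory.

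The two documents treat plasma concentration and early hearing differently:

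- **SAP 7.1.3, analysis of variance.** The variables include "normalized values (Z-scores) of drug plasma concentration", and "Z-scores of hearing functions measured immediately following surgery will be included in the analysis of variance". No response variable is named.
- **SAP 7.1.3, first CEP-SKAT analysis**, meant to show that variants are specific to zonisamide response: "Age, gender, drug concentration, and noise duration and intensity will be adjusted for the analysis".
- **SAP 7.1.3, later sentence**, after the two-week, 30-day, ECochG and WIN analyses are introduced: "To control for confounding effects, these models will be adjusted for age, gender, and noise duration and intensity".
- **Protocol 12.5, opening step.** A univariate logistic screen looks for "potential confounding variables: sex, age, Z-scores of drug concentration", with noise exposure and early hearing further down the same list.
- **Protocol 12.5, the same CEP-SKAT step:** "Age, gender, and noise duration and intensity will be adjusted for the analysis".

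Neither document states covariates for the single-marker logistic models.

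**The concern.** A confounder is a common cause of exposure and outcome. Plasma zonisamide cannot play that role for CYP2C9 or CYP2C19, because genotype is fixed before the drug is given and these genes were chosen for their part in its metabolism. Concentration is a consequence of genotype, and the main route by which a metabolism gene would be expected to change hearing outcome. Conditioning on it takes out the effect being sought.

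Early hearing raises the same question for other markers. The only hearing test scheduled immediately after surgery is the recovery DPOAE, within 8 hours. It measures early cochlear change, so it is plausibly downstream of noise-susceptibility genotype and of a pre-op dose.

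The Protocol's univariate screen does not protect against this. It selects variables associated with the outcome, and a strong mediator will tend to pass.

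At stake is whether a real metabolism-gene effect is reported as null in the analysis meant to inform genotype-based dosing. The conflicting lists add a second problem: an analyst could choose between them after seeing results.

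**Working it through.** **No plan figure to reproduce.** Neither document gives a power, effect size, allele frequency or significance level for the genetic analysis. Every genetic input below is an assumption. From the documents come only the 234 subjects in three equal arms, hence 234/3 = 78 per arm and 2 × 78 = 156 on zonisamide. The documents do not say which subjects enter CEP-SKAT, so 156 is itself an assumed analysis set.

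**Model.** Let G be the minor-allele count (frequency m), E true exposure, C measured concentration and Y the threshold shift, with full mediation:

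- E = aG + e, with Var(e) = 1
- C = E + u, with Var(u) = 1/λ − 1, so λ is the reliability of C within genotype
- Y = −cE + noise, with noise variance 1 − c²

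Unadjusted, the coefficient of G is −ac. Given G, the slope of Y on C is −cλ. The adjusted coefficient of G is therefore −ac + cλa = −ac(1 − λ), so adjustment retains a share 1 − λ of the effect: 0, 20%, 50% and 80% at λ = 1.0, 0.8, 0.5 and 0.2.

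**Hand check, n = 156, m = 0.30, a = 0.7, c = 0.5.**

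- Unadjusted effect: 0.7 × 0.5 = 0.35. Var(G) = 2 × 0.30 × 0.70 = 0.42 and residual variance is 1, so SE = 1/√(156 × 0.42) = 0.1235 and z = 2.83. Power at two-sided 0.05 is Φ(2.83 − 1.96), about 81%.
- Adjusted, λ = 0.8: effect 0.35 × 0.2 = 0.07. Residual variance is 1 − 0.25 × 0.8 = 0.80. Var(C) = 0.49 × 0.42 + 1.25 = 1.456, so Var(G given C) = 0.42 × (1 − 0.206/1.456) = 0.361. SE = √(0.80/(156 × 0.361)) = 0.119 and z = 0.59. Power is about 9%.

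**Simulation.** Linear regression, 1,500 runs per cell, two-sided 0.05 for one marker. Monte Carlo error is at most √(0.25/1500), or 1.3 points.

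| n | m | a / c | Unadjusted | λ = 1.0 | λ = 0.8 | λ = 0.5 | λ = 0.2 |
|---|---|---|---|---|---|---|---|
| 156 | 0.30 | 0.7 / 0.5 | about 80% | 5% | 9% | 29% | 61% |
| 156 | 0.30 | 1.0 / 0.7 | about 100% | 5% | 25% | 83% | 99% |
| 156 | 0.15 | 0.7 / 0.5 | 56–59% | 6% | 8% | 20% | 39% |
| 78 | 0.30 | 0.7 / 0.5 | about 50% | 5% | 8% | 18% | 37% |

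The last four columns are power after adjusting for C. If a direct path of equal size (0.35) is added to the first row's inputs, half the effect survives even at λ = 1.0, and adjusted power is 83%.

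**Which λ applies?** The documents point away from 1.0. There is one concentration sample, timed from the first capsule: within 12 hours in the Protocol calendar, at 12 hours in the SAP calendar note. In the post-op arm that capsule is placebo, so the sample may precede the active dose or follow it by a variable interval.

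**Limits.** This is a single-marker linear model, not CEP-SKAT itself. A threshold corrected for several markers would lower both adjusted and unadjusted power. The early-hearing path was not simulated.

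**The case against.** The strongest reply is that much of the plan already avoids the problem. Protocol 12.5 leaves concentration out of the CEP-SKAT step. The later SAP sentence, on its natural reading, leaves it out of the two-week, 30-day, ECochG and WIN models. The single-marker models have no stated covariates, and early hearing is in no CEP-SKAT list. All of this stands: a reader might infer that every genetic model is affected, and the documents do not support that.

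A poorly measured concentration also blocks only part of the path. That is correct and rules out a claim of total loss, but it is not a defence of the covariate. Concentration should be nil on placebo and depends on sampling time in the post-op arm, so it partly encodes arm and timing, and the adjusted coefficient is hard to interpret.

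Conditioning on exposure can also be legitimate. For response variants unrelated to metabolism, asking whether genotype matters at a given drug level is a sensible question. This stands, and it is why concentration should not be barred from every model.

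Finally, nothing in the documents shows that susceptibility genes act mainly through the injury that recovery DPOAE detects. Protocol 1.2 describes synaptic injury that leaves thresholds unchanged at first. The early-hearing part is therefore a plausible risk of unknown size.

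**Conclusion.** The point holds in limited form. SAP 7.1.3, followed as written, adjusts one CEP-SKAT analysis and an undefined analysis of variance for a variable downstream of the metabolism genes. The analysis of variance also includes a measure plausibly downstream of the susceptibility genes and of pre-op drug. The resulting attenuation for CYP2C9 and CYP2C19 could be small or complete. Under full mediation it equals the reliability of the concentration measure, and the power figures rest on assumed allele frequencies and effects.

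A reader might infer that the trial cannot detect its metabolism markers. That would need full mediation, error-free exposure and the same adjustment in every model. The sampling scheme contradicts the second condition and the other covariate lists contradict the third.

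The conflict between the lists needs no assumptions: the SAP's CEP-SKAT step includes concentration, while the same step in the Protocol and a later SAP sentence do not. The primary efficacy conclusion is untouched. Genotype and drug level are both collected, so nothing is lost irretrievably, and SAP 2.2.3 requires validation in a later study before any dosing use.

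**What to change.** Before genetic data are analysed, amend SAP 7.1.3 and Protocol 12.5 together:

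1. Give one covariate list for each model, including the single-marker models, and name the response variable and analysis set for each.
2. Make the main genotype-outcome models adjust only for age, sex and noise exposure, without concentration or immediate post-surgery hearing. Remove those two from the Protocol's confounder screen.
3. Add a model of zonisamide concentration on CYP2C9 and CYP2C19 genotype in zonisamide recipients, allowing for arm and time since the active dose. Neither document states such a model, although it is the most direct test of the metabolism markers.
4. Keep any model adjusted for concentration or early hearing as a secondary analysis, labelled as mediation or as conditional on exposure.

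The cost is wording in two documents and one extra model. No new data or software are needed, although step 3 depends on the sampling and dosing times being recorded.

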## 5.5 Follow-Up Assessments

The follow-up assessments will occur after surgery and include the following tests or procedures:

- 1. DPOAE testing in recovery, within 8 hours after surgery.
- 2. Blood samples taken within 12 hours following the first pill for PGx surveys.
- 3. Collection of laboratory test results for research purposes that include an electrolyte panel, BUN, Cr, ALT, and AST. If these tests are not performed as part of clinical care post-operatively, we will obtain them for research purposes at the time of the PGx blood draw.
- 4. DPOAE, Audiogram, ECochG, and WIN testing 30 days (+/-3 days) after surgery.
- 5. Completion of the Hearing History and Occupation Exposure questionnaire 30 days (+/- 3 days) after surgery.
- 6. Documentation of adverse events.

Follow-up assessments will be planned at the stated time points; actual follow up times may vary due to patient logistics and compliance.

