3.3 Secondary efficacy outcomes

The secondary outcome measures are key audiological and clinical assessments of hearing loss as listed below as continuous level variables.

- DPOAE: Distortion product otoacoustic emissions will be measured at baseline (before surgery), as well as within 8 hours and at 30 days (+/- 3 days) post-surgery to measure both temporary and permanent change in DPOAE amplitude relative to baseline. A change is noted in DPOAE amplitude at any frequency that is significantly greater than the stability of each measurement (i.e., 95% confidence interval of each measurement do not overlap).
- ECochG: Electrocochleography will be measured at baseline (before surgery) and at 30 days (+/- 3 days) post-surgery to measure change in ECochG AP amplitude, latency, and width.
- WIN testing: The Words in Noise Test will be administered at baseline (before surgery) and at 30 days (+/- 3 days) after surgery. The respective scores will be converted to Z-scores to evaluate any change in scores relative to baseline.

The study will also include an exploratory analysis aiming to identify biomarkers of response to ZNS.

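### The pharmacogenetics plan names a two-week time point that no visit collects and two cohorts that it never defines, and it states no genotype-by-arm term although it looks for variants tied to ZNS protection

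*SAP*

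**What the plan says.** Protocol 2.2 makes the genetic work a secondary objective: "To identify a genetic risk profile associated with drilling-induced hearing loss we will survey known genetic markers", followed by named genes for noise-induced hearing loss and for ZNS metabolism. SAP 2.2.3 repeats the text but labels it exploratory.

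The analysis itself is one paragraph, nearly identical in Protocol 12.5 and SAP 7.1.3. It starts from the aim of finding variants linked to ZNS protection. It runs single-marker logistic regression on two imputed data sets, and then: "We will combine association results in the two cohorts by performing" a genome-wide, inverse-variance, fixed-effect meta-analysis. CEP-SKAT follows, to check whether the variants are specific to ZNS response. Then comes a repeat: "The analysis will also be performed using hearing data collected two weeks following surgery". The next sentence describes that repeat as using ECochG and WIN measures and "using average audiogram threshold shifts and DPOAE amplitudes at 30 days (+/- 3 days) post-treatment". The paragraph closes with Bonferroni-adjusted post hoc comparisons of control and ZNS-treated subjects.

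The testing schedule is in Protocol 5.5: "DPOAE testing in recovery, within 8 hours after surgery" and "DPOAE, Audiogram, ECochG, and WIN testing 30 days (+/-3 days) after surgery". SAP 3.3 agrees. DPOAE is taken at baseline, "as well as within 8 hours and at 30 days (+/- 3 days) post-surgery". For ECochG, "Electrocochleography will be measured at baseline (before surgery) and at 30 days (+/- 3 days) post-surgery", and WIN has the same two time points.

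**The concern.** An analyst given this paragraph has to guess three things: which visit supplies the repeat analysis, what the two cohorts and two imputed data sets are, and which model term measures a genetic difference in response to ZNS. The last matters most. A variant that makes an ear more vulnerable to drill noise and a variant that changes the benefit from ZNS can both be associated with threshold shift. Only a comparison of genotype effects between arms tells them apart.

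The analysis is to be done after the trial by a separate company, so each gap becomes a choice made with the data in hand. Protocol 1.4 intends the results for discussion with FDA, and Protocol 2.2 looks ahead to dosing by genetic profile if associations are validated. A susceptibility variant mistaken for a response variant would mislead that later work.

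**Working it through.** The plan gives no effect size, marker count or power for the genetic analysis, so there is no figure to reproduce. The check compares passages and then works through what the stated pooling would estimate.

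**1. Time point.**

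| Source | Hearing data after surgery |
|---|---|
| Protocol 5.5 and 9.0 | DPOAE within 8 hours; full battery at 30 days (+/- 3) |
| SAP 3.3 | DPOAE within 8 hours; DPOAE, ECochG and WIN at 30 days (+/- 3) |
| SAP 7.1.3 and Protocol 12.5, repeat analysis | two weeks, then 30 days in the next sentence |

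The 30-day window is 30 − 3 = day 27 to 30 + 3 = day 33. Nothing is scheduled near day 14; the nearest later test opens 27 − 14 = 13 days afterwards. The two-week windows elsewhere (Protocol 6.0 and 8.0; SAP 4.3 and 8.1.1) are for adverse events.

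**2. Cohorts.** The trial has three arms of 78 (234 in all) and recruits from one institution's clinics. No second or external cohort is named for the genetic analysis. Two readings are possible. Let β be the genotype effect within an arm, b a pure susceptibility effect (equal in all arms) and d an added effect under ZNS only. Assume that variance is inversely proportional to sample size.

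- *The two ZNS arms.* Pooled effect = (β_pre + β_post)/2 = b + d. Placebo is absent, so b cannot be subtracted.
- *Any ZNS (156) versus none (78)*, the contrast in the last step of Protocol 12.5. Weights are 156/234 = 2/3 and 78/234 = 1/3. Pooled effect = (2/3)(b + d) + (1/3)b = b + (2/3)d. A pure response variant (b = 0) gives 2d/3, exactly what a pure susceptibility variant with b = 2d/3 would give.

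Under either reading the pooled estimate mixes b with d. The quantity of interest, d = β_ZNS − β_placebo, is not estimated.

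**3. Model terms.** The later adjustment lists contain age, gender, noise duration and noise intensity; the SAP adds drug concentration once. Neither arm nor genotype-by-arm appears. Drug concentration does not replace arm. The ZNS sample is tied to the first dose (within 12 hours of it in Protocol 9.0, 12 hours after it in SAP 2.6). In the post-op arm the first dose is placebo (Protocol 5.2), so the sample may precede active drug.

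**4. Hearing just after surgery.** Protocol 12.5 screens it as a potential confounder, and SAP 7.1.3 includes it in the analysis of variance. The later adjustment lists omit it. Protocol 2.2 hypothesises that pre-op ZNS prevents temporary cochlear change, so this variable may already carry a treatment effect.

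**5. Precision of the interaction.** Let V₁ and V₂ be the variances of the genotype effect in a ZNS arm and in placebo. The difference has variance V₁ + V₂, and the inverse-variance pooled effect has V₁V₂/(V₁ + V₂). The ratio is (V₁ + V₂)²/(V₁V₂), which is at least 4. The interaction's standard error is therefore at least √4 = 2 times that of the pooled genotype effect in the same 156 subjects. The trial was sized for the arm comparison (stated power 80.4%; exact enumeration gives 80.7%), not for this.

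**The case against.** The strongest reply is that this is a drafting slip in exploratory work. The sentence after the two-week phrase lists measures that are all collected at 30 days, so the intended visit is fairly clear. That stands. A reader might infer that the genetic analysis cannot be run at all; the documents do not support this. Single-marker regression and CEP-SKAT can use the 30-day data, and the 8-hour DPOAE supplies an immediate measure.

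The calendar in SAP 2.6 heads its last column as within 30 days, which might seem to admit a day-14 test. SAP 3.3 and both Protocol schedules fix the visit at 30 days (+/- 3), and there is only one such battery per subject.

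A reader might also infer that the two cohorts are impossible in this trial. The supportable statement is that they are undefined: they could be the two ZNS arms, or any ZNS versus none. Nor do the two imputed data sets clearly conflict with the 10 imputations planned for the primary endpoint, since the reference to allele dosage suggests genotype imputation.

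On ZNS response, the plan does have a confirmation step, a drug-concentration variable and closing control-versus-ZNS comparisons, and it nowhere says that arms are pooled in the single-marker model. Main-effect association also serves the risk-profile objective. That much stands, but none of these steps states a genotype contrast between arms.

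Finally, it would go too far to say that the association models adjust for post-surgery hearing. Its role is ambiguous: it is a screening or analysis-of-variance variable, and may be the first-pass outcome.

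**Conclusion.** The point holds as a defect of specification. One named time point has no scheduled data and is contradicted by the following sentence. The cohorts and imputed data sets are undefined in both documents. The association models as stated do not separate susceptibility from response to ZNS, and under either plausible reading of the cohorts the fixed-effect pooling would not separate them either. That last step rests on those two readings and on the weights assumed above; a different definition of the cohorts would need its own check.

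The consequence is limited. The primary endpoint, alpha and sample size are untouched, and the SAP calls this work exploratory although the Protocol lists it as secondary. The effect on genetic estimates cannot be sized from the documents. This is a correction worth making, not a threat to the trial's main conclusion.

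**What to change.** Rewrite the paragraph in both Protocol 12.5 and SAP 7.1.3:

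1. Replace the two-week time point with the 30-day (+/- 3) visit.
2. Define the two cohorts and the two imputed data sets, or delete them together with the meta-analysis.
3. For the listed candidate markers, add arm and arm-by-genotype terms to the single-marker model, with placebo as reference. Report the interaction estimates with confidence intervals as exploratory, given the low power for interaction.
4. State that hearing measured just after surgery (DPOAE only) is an outcome and not an adjustment covariate, because pre-op ZNS may already have changed it.

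The cost is one paragraph in each document. No new data, visits or subjects are needed.
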